STUDY DESIGN General This open-label extension study will evaluate the safety of long-term twice-monthly administration of somavaratan in adults with GHD. This is an open-label, multicenter study open to subjects completing a Versartis adult GHD study as well as approximately 40 new somavaratan naïve subjects (either rhGH treatment naïve or currently receiving daily rhGH therapy). All subjects will receive twice-monthly (every 15 days \pm 2 days) subcutaneous (SC) somavaratan. Doses will be titrated to each subject's individual IGF-I responses based on the IGF-I level 7 days post-dose until a maintenance dose is achieved. Maintenance dose is defined as an IGF-I value between 0 and 2.0 SDS for two consecutive 7 day post-dose time points (Day 8, peak level). Subjects receiving somavaratan once-monthly in this study (Protocol 15VR8) or in a previous somavaratan study (Protocol 15VR7), will have their dose decreased by half (minimum dose of 20 mg, 40 mg for women on estrogen, rounded down to the nearest even number) and will be titrated per the Dose Titration Plan (Table 2). New subjects enrolling in this study will be assigned to one of two cohorts and will receive a starting dose of 20 mg twice-monthly (40 mg for women on estrogen) (Table 1) and will be

titrated per the Dose Titration Plan (Table 2). Maintenance doses may be adjusted further based on PD data at the discretion of the Investigator or Medical Monitor.

Table 1 Study Drug Starting Dose Information:

Subject Cohort Assignment	Fixed Starting Study Dose	Frequency of Administration
Cohort 1: Adults with GHD irrespective of age and gender	20 mg	Twice-Monthly
Cohort 2: Women receiving oral estrogens	40 mg	Twice-Monthly

Table 2 Dose Titration Plan

Downward Dose Titration		
IGF-I at Day 8	Cohort 1	Cohort 2
0 to 2.0 SDS	No change in dosing	No change in dosing
2.01 to 3.0 SDS	4 mg dose decrement	4 mg dose decrement
Greater than 3.0 SDS	10 mg dose decrement	10 mg dose decrement
Upward Dose Titration ¹		
IGF-I at Day 8	Cohort 1	Cohort 2
-1.0 to 0 SDS	4 mg dose increment	10 mg dose increment
Less than -1.0 to -2.0 SDS	10 mg dose increment	20 mg dose increment
Less than -2.0 SDS	20 mg dose increment	40 mg dose increment

1: Maximum allowable dose is 250.0 mg

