Despite dose adjustments (reductions), of the 29 subjects that completed 5 doses in the Phase 2 study at the time of this protocol amendment, IGF-I values 7 days after the last (fifth) dose were > 2.0 SDS in 16 subjects (55%) and > 3.0 SDS in 7 subjects (24%).

Based on these findings, it was determined that:

- A lower starting dose is needed
- The maintenance doses in rollover subjects seems to be too high, and a lower maintenance dose is needed
- The dose titration plan was not adequate to address the high IGF-I levels at Day 8 and a new titration plan based solely on IGF-I SDS 7 days after dosing is proposed
- The dosing frequency should be revised to twice-monthly to allow for adequate response during the dosing interval with reduced IGF-I excursions above 2.0 SDS
- Dosing initiation and titration should be made on a fixed (mg) basis and not be based upon-body weight adjusted (mg/kg) basis

Starting Dose

Evaluation of the doses resulting in Day 8 IGF-I above and below 2.0 SDS indicate that for adult subjects with GHD (except women receiving estrogens), 20 mg was the lowest dose that did not result in a response > 2.0 SDS in 90% of the subjects. For women receiving estrogens, a similar analysis was performed and the identified starting dose was 40 mg.

A fixed starting dose regardless of weight, age and gender is therefore planned for this study:

- 20 mg for all subjects other than women receiving oral estrogen
- 40 mg for women receiving oral estrogen

Dosing Frequency

Data from the ongoing analysis of the Phase 2 study have shown that the pre-dose (trough) IGF-I levels were similar to the baseline IGF-I levels (prior to any somavaratan exposure), suggesting that the duration of effect was less than one month. In addition, after the last (fifth) dose of somavaratan in the Phase 2 study, IGF-I levels at 21 days after dosing had already diminished to values not different than the pre-dose levels. Based on this analysis, the planned dosing frequency for this study is:

- Twice-Monthly

Continued Dosing in Rollover Subjects Presently Participating in This Study

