3 INVESTIGATIONAL PLAN

3.1 Overall Study Design and Plan

This open-label extension study will evaluate the safety of long-term twice-monthly administration of somavaratan in adults with GHD. This study is open to subjects completing a Versartis adult GHD study as well as approximately 40 new somavaratan naïve subjects (either rhGH treatment naïve or currently receiving daily rhGH therapy). A total of up to 250 subjects may be enrolled in this study. All subjects will receive twice-monthly (every 15 days \pm 2 days) subcutaneous (SC) somavaratan. All subjects will have somavaratan doses titrated per the Dose Titration Plan (Table 2) to each subject's individual IGF-I responses based on the IGF-I level collected 7 days post-dose (Day 8) until a maintenance dose is achieved. Maintenance dose is defined as an IGF-I value between 0 and 2.0 SDS for two consecutive 7 day post-dose time points (peak).

Subjects receiving somavaratan once-monthly in this study (Protocol 15VR8) or in a previous somavaratan study (Protocol 15VR7), will have their dose decreased by half (minimum dose of 20 mg, 40 mg for women on estrogen, rounded down the nearest even number) and will be titrated per the Dose Titration Plan (Table 2).

New subjects naïve to somavaratan treatment enrolling in this study will be assigned to one of two cohorts and will receive a starting dose of 20 mg twice-monthly (40 mg for women on estrogen) (Table 1) and will be titrated per the Dose Titration Plan (Table 2).

Maintenance doses may be adjusted further at the discretion of the Investigator or Medical Monitor while maintaining IGF-I at Day 8 (7 days post dose) within target range. For patients on maintenance dose that have IGF-I levels $>$ 2.0 SDS at any point during the maintenance period, dose adjustment shall be made by the Investigator or Medical Monitor based on clinical judgment with the objective to achieve and maintain IGF-I at day 7 post-dose between 0 and 2.0 SDS. Any change in somavaratan dose in a subject that has achieved maintenance dosing will be followed by an ad-hoc Day 8 IGF-I measurement to ensure IGF-I values are within target range (0 and 2.0 SDS).

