Study visits/blood sample collections will occur every week during the first month of the study, followed by monthly clinic visits until the subject has reached maintenance dose. Once maintenance dose is achieved, in clinic visits will occur quarterly during the first year. Although quarterly visits will continue throughout the study, after the first year blood samples will be collected every 6 months, with intervening visits used for brief physical exams and collection of AEs and concomitant medications.

In current clinical practice with daily rhGH products, individualized dose titration is the standard of care. Daily rhGH doses are titrated to achieve normalization of IGF-I (the primary PD parameter) without jeopardizing safety. Each patient may have different IGF-I and safety

responses to daily rhGH treatment, especially with regards to potential adverse events such as edema. The IGF-I response to rhGH depends on many factors. One of the mostly recognized is the exposure to estrogens, in particular oral estrogens, which confers relative resistance to rhGH. Consequently, subjects will be stratified into the following two cohorts:

- Cohort 1: adults with GHD irrespective of age and gender will receive a starting dose of 20 mg twice-monthly
- Cohort 2: women receiving oral estrogen will receive a starting dose of 40 mg twice-monthly

Subjects entering the study currently receiving daily rhGH treatment must have discontinued rhGH for a minimum of 14 days prior to initiating treatment with somavaratan. Additionally, these subjects must have a baseline IGF-I SDS ≤ 0 .

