4.2 Treatments Administered

All subjects will receive somavaratan twice-monthly.

- Subjects receiving somavaratan once monthly in a prior Versartis adult GHD study or in this study, irrespective of the cohort assignment and whether they have achieved maintenance dosing, will transition to receive treatment at half of their current dose (rounded down to the nearest even number, minimum dose of 20 mg).
- New subjects naïve to somavaratan will be assigned to one of two treatment cohorts (Table 1) with different starting doses based on the subject's use of oral estrogens. The initial dose will be a fixed dose.

All subjects will have Day 8 IGF-I SDS evaluated each month with subsequent dose adjustments made per the Dose Titration Plan (Table 2).

Table 1 Study Drug Starting Dose Information

Subject Cohort Assignment	Fixed Starting Study Dose	Frequency of Administration
Cohort 1: Adults with GHD irrespective of age and gender	20 mg	Twice-Monthly ¹
Cohort 2: Women receiving oral estrogens	40 mg	Twice-Monthly ¹

1: Allowable dosing window is every 15 days ± 2 days

Table 2 Dose Titration Plan

Downward Dose Titration		
IGF-I at Day 8	Cohort 1	Cohort 2
0 to 2.0 SDS	No change in dosing	No change in dosing
2.01 to 3.0 SDS	4 mg dose decrement	4 mg dose decrement
Greater than 3.0 SDS	10 mg dose decrement	10 mg dose decrement
Upward Dose Titration¹		
IGF-I at Day 8	Cohort 1	Cohort 2
-1.0 to 0 SDS	4 mg dose increment	10 mg dose increment
-1.0 to -2.0 SDS	10 mg dose increment	20 mg dose increment
Less than -2.0 SDS	20 mg dose increment	40 mg dose increment

1: Maximum allowable dose is 250.0 mg

The starting doses and Dose Titration Plan (Tables 1 and 2) may be altered by the Sponsor based on continued evaluation of the Phase 2 data and/or data gathered during this study. Adjustments may be implemented to alleviate safety concerns or optimize normalization of IGF-I SDS responses. The Investigator and Medical Monitor may agree to temporarily alter or suspend a subject's dose during illness or injury.

If a subject on maintenance dose has an IGF-I value outside the target range, further dose adjustments will be considered on an individual basis by the Investigator or Medical Monitor with the objective to achieve and maintain IGF-I SDS at Day 8 within target range (IGF-I SDS between 0 - 2.0)

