Appendix 2 Definition of Childbearing Potential and Contraceptive Requirements

The risks of treatment with somavaratan during pregnancy have not been evaluated. Please refer to the latest version of the Investigator's Brochure for additional information.

1) Definition of Female of Childbearing Potential

Women < 54 years of age with amenorrhea of any duration will be considered to be of childbearing potential unless they have had a hysterectomy, bilateral oophorectomy, or medically documented ovarian failure.

Women \geq 54 years of age with cessation of menses for \geq 12 months will not be considered to be of childbearing potential.

2) Contraceptive Requirements for Females

Female subjects of childbearing potential must agree to use a highly effective method of contraception from the enrollment visit through 30 days after the last dose of somavaratan. The Investigator should counsel subjects on appropriate methods for avoiding pregnancy during the study. These methods are recommended due to a low failure rate (<1% per year), and include the following:

Single methods: Copper or LNG Intrauterine Device (IUD), progesterone implant or injection, tubal sterilization*, or vasectomy with documented azospermia 3 months post-procedure

Combination methods: oral contraceptives plus barrier, transdermal patch plus barrier, vaginal ring plus barrier, diaphragm with spermicide plus condom

Abstinence is only considered an acceptable method of contraception if it is a pre-existing part of a subject's lifestyle. Symptom-thermal methods (basal body temperature, cervical mucous, or calendar/rhythm) or withdrawal are not considered adequate forms of contraception for the purposes of this study.

*Tubal sterilization via the Essure procedure is not considered a reliable form of contraception unless tubal blockage is verified by hysterosalpingogram (HSP) approximately 3 months after microinsertion. Prior to verification, another contraception method described above should be used.

3) Contraceptive Requirements for Male Subjects (and their female partners)

All male study participants must agree to consistently and correctly use a condom from Baseline until 90 days after administration of the last dose of study drug. If their female partner is of childbearing potential (as defined above), their female partner must use 1 of the methods of birth control listed above from the date of Screening until 90 days after administration of the last dose of study drug.

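### The estrogen criterion behind the 40 mg starting dose and the rollover minimum is stated inconsistently, and for rollover women on estrogen the sections give minimums of 40 mg and 20 mg with nothing to decide between them

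*Combined protocol and SAP*

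**What the plan says.** The higher dose is described in three ways in the current protocol text.

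- **No route stated.** For new subjects, Section 3.1 (Overall Study Design and Plan) says they "will receive a starting dose of 20 mg twice-monthly (40 mg for women on estrogen) (Table 1"). The Synopsis (Study Design) has the same rule. For subjects moving from once-monthly dosing, the Synopsis halves the dose subject to a "minimum dose of 20 mg, 40 mg for women on estrogen, rounded down to the nearest even number". Section 3.1 repeats this almost word for word.
- **Oral only.** Further on, Section 3.1 defines the cohorts: "Cohort 1: adults with GHD irrespective of age and gender will receive a starting dose of 20 mg twice-monthly" and "Cohort 2: women receiving oral estrogen will receive a starting dose of 40 mg twice-monthly". Table 1, in the Synopsis and in Section 4.2, labels the 40 mg row "Cohort 2: Women receiving oral estrogens". The Synopsis study population text also says oral. Section 3.3 and the new-subject bullet of Section 4.2 give oral estrogen use as the basis for the dose.
- **No estrogen exception.** For rollover subjects, Sections 4.2 and 5 halve the dose whatever the cohort and give a single minimum of 20 mg.

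**The concern.** Estrogen use selects a dose, so the criterion has to read the same wherever it appears. Section 3.1 also indicates that route matters, because it singles out oral estrogens among estrogens as the cause of relative resistance to growth hormone.

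Women on non-oral estrogen can enter the trial. Inclusion criterion 6 allows stable hormone replacement without limiting the route.

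The first dose or rollover dose of an individual woman is at stake, in a study amended because doses were too high. The Version 2 rationale reports Day 8 IGF-I above 2.0 SDS in 19 of 36 Phase 2 subjects (53%) after the first dose. Under Section 3.5.1, two consecutive Day 8 values of 3.0 SDS or more despite dose adjustments lead to withdrawal. Evaluating the starting dose, the maintenance dose and the titration plan is a secondary objective, and Section 8.1 presents all summaries by cohort.

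**Working it through.** The protocol has no calculation on this point to reproduce. The check compares the statements and applies each to the same woman.

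**Inputs.** Starting doses of 20 and 40 mg (Table 1); rollover minimum of 20 mg, or 40 mg for women on estrogen (Synopsis, 3.1); rollover minimum of 20 mg (4.2, 5); the rounding rule and the 54 mg worked example (Version 2 rationale); up to 250 subjects, about 40 of them new (3.1).

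**Step 1: new subject on non-oral estrogen.**

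| Text followed | First dose |
|---|---|
| Synopsis and 3.1 sentence, read literally | 40 mg |
| Table 1 and cohort definitions | 20 mg |

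Ratio: 40/20 = 2. The sentence speaks of assignment to one of two cohorts and cites Table 1, and both specify oral estrogen. Following the reference resolves the conflict in favour of the table. For a new subject on oral estrogen all the statements agree on 40 mg.

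**Step 2: rollover woman on estrogen.** Let M be the once-monthly dose in mg. Halving and rounding down to an even number gives H = 2 × floor(M/4), and the new dose is the larger of H and the minimum. The protocol's example reproduces: M = 54 gives 54/2 = 27, rounded down to H = 26.

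| Case | Minimum 40 mg (Synopsis, 3.1) | Minimum 20 mg (4.2, 5) | Ratio |
|---|---|---|---|
| H of 20 mg or less | 40 mg | 20 mg | 40/20 = 2 |
| H = 26 mg (M = 54) | 40 mg | 26 mg | 40/26 = 1.54 |
| H of 40 mg or more | H | H | 1 |

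The two minimums give different doses whenever H is below 40 mg, that is, for a once-monthly dose below 2 × 40 = 80 mg. The gap is at most two-fold.

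**Step 3: is there a tie-break for rollovers?** The rollover sentence in the Synopsis and 3.1 refers only to Table 2. That table has cohort columns but does not define the cohorts and contains no minimum dose. Sections 4.2 and 5 do not mention estrogen in the rollover rule and apply it regardless of cohort. The conflict therefore covers women on oral estrogen as well as those on other routes. For a woman on oral estrogen, inserting the word oral in the Synopsis and 3.1 would leave 40 mg there and 20 mg in Sections 4.2 and 5.

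**Step 4: how many women?** With up to 250 subjects and about 40 new, rollovers could number up to about 250 − 40 = 210. The documents do not say how many are women on estrogen, by what route, or at what monthly dose, so this figure only bounds the group in which the rollover conflict can occur.

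**The case against.** The strongest reply is that this is a dropped word. No sentence defines Cohort 2 as anything other than oral estrogen, the new-subject sentence cites the table that says so, and in the Synopsis the table follows directly. The Version 2 rationale, which is amendment background and not operative text, states both the starting dose and the rollover minimum with the word oral. It does describe the underlying dose analysis without a route ("For women receiving estrogens, a similar analysis was performed and the identified starting dose was 40 mg"), but little weight can rest on that. The Medical Monitor also reviews history and Screening results before each enrolment (4.3), and no hypothesis test is planned.

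For new subjects this largely stands: the fault is one of wording, and a careful reader would find the oral reading.

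It does not stand for rollovers. The absence of any estrogen exception in Sections 4.2 and 5 cannot be explained by a missing word elsewhere, and no cross-reference settles it. Section 4.3 describes the Medical Monitor's review as a decision on enrolment and does not expressly cover cohort assignment or the minimum dose.

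It is also fair to object to using the contraceptive list in Appendix 2 ("oral contraceptives plus barrier, transdermal patch plus barrier, vaginal ring plus barrier") as proof that non-oral estrogen users will enrol. The documents do not say that the patch or ring contains estrogen, so that is an assumption. The point does not need it, because inclusion criterion 6 already leaves the route of hormone replacement open.

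**Conclusion.** The inconsistency is real and should be fixed. For new subjects on non-oral estrogen the literal sentences and Table 1 differ two-fold (40 against 20 mg), but the reference to Table 1 and the uniform cohort definitions point to one reading. For rollover women on estrogen by any route the sections conflict outright: the minimum is 40 or 20 mg, and the resulting dose differs by up to two-fold when the halved dose is below 40 mg.

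A reader might go further and infer that a woman on non-oral estrogen belongs to Cohort 1 by one sentence and Cohort 2 by another. On that view she would also get different upward steps in Table 2 (4 or 10 mg, 10 or 20 mg, 20 or 40 mg), could be at 20 + 20 = 40 mg or 40 + 40 = 80 mg after one step for Day 8 IGF-I below -2.0 SDS, and would blur the by-cohort summaries. The documents do not support this as it stands. Table 2 is keyed to cohort, and every cohort definition says oral. Those consequences arise only if a site assigns cohort from the unqualified wording.

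The conclusion assumes that at least some enrolled women use estrogen, which the existence of Cohort 2 implies. The number affected is not given. No view is taken on which dose or criterion is right.

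**What to change.** The sponsor should reconcile the passages by adopting one estrogen criterion that names the route. It should appear in identical words for the starting dose, the rollover minimum and cohort assignment in the Synopsis, Section 3.1, Section 4.2 with Table 1, and Section 5. Sections 4.2 and 5 must agree with the Synopsis and 3.1 on whether the rollover minimum has an estrogen exception.

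The cohort and minimum dose of women already enrolled should then be checked against that criterion, using the concomitant medication data already collected. The documents do not say whether route is recorded with each medication. Where it is not, it would have to be taken from source records.

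The cost is a wording change in an amendment or clarification letter and a one-time check of existing records. No new procedures or visits are needed.

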Immunogenicity will be assessed by screening for anti-drug antibodies (ADAs) at baseline and every 3 months during the first year and every 6 months thereafter. ADAs will be measured on blood samples collected at troughs (pre-dose). Testing will follow a tiered approach consisting of screening, confirmation, titration, and additional characterization of confirmed ADA positive samples.

STATISTICAL METHODS

Safety data will be listed by subject and summarized by cohort using frequencies or descriptive statistics. All subjects who receive at least one dose of somavaratan will be included in the safety analysis. Summaries of all adverse events (AEs), serious adverse events (SAEs), and incidence of Grade 3 or 4 adverse events will be classified according to severity and relationship to study drug.

No formal hypothesis testing is planned for this extension study.

For continuous variables, descriptive statistics will include the number of subjects, mean, standard deviation (SD), median, minimum, and maximum. For categorical variables, descriptive statistics will include the number and percentage of subjects in each category.

Summaries of subject disposition, demographics, disease characteristics, and exposure and response to dosing of study medication will be provided.

Somavaratan ADAs will be summarized descriptively.

AEs, PK, and PD will also be descriptively summarized by ADA subgroup (positive, negative) to assess potential effects of ADA positivity.

TABLE OF CONTENTS

APPROVAL/SIGNATURE PAGE: SPONSOR AND CONTRACT RESEARCH ORGANIZATION	2
SYNOPSIS: PROTOCOL 15VR8.....	3
LIST OF ABBREVIATIONS AND DEFINITIONS OF TERMS.....	15
1 INTRODUCTION	22
1.1.1 Adult Growth Hormone Deficiency.....	23
1.1.2 Pediatric Growth Hormone Deficiency	24
1.1.3 Summary of Clinical Experience	26
2 STUDY OBJECTIVES.....	28
2.1 Primary Objective.....	28
2.2 Secondary Objectives.....	28
3 INVESTIGATIONAL PLAN.....	29
3.1 Overall Study Design and Plan.....	29
3.2 Rationale for Study Design.....	31
3.3 Dose Selection	31
3.4 Study Duration and Dates.....	32
3.5 Safety Review and Stopping Rules.....	32
3.5.1 Stopping Rules.....	32
STUDY POPULATION SELECTION	33
3.6 Study Population.....	33
3.7 Inclusion Criteria:	33
3.8 Exclusion Criteria:	34
3.9 Subject Withdrawals and Replacements.....	35
4 STUDY TREATMENT(S).....	36
4.1 Description of Treatment(s).....	36
4.1.1 Somavaratan Treatment	36
4.2 Treatments Administered.....	36
4.3 Selection and Timing of Dose for Each Subject.....	37

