5.7.2 Timing

Recording of AEs should begin after informed consent is obtained. AEs occurring after study drug administration are treatment emergent AEs.

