6.1.3 First Month Procedures

All subjects will begin twice-monthly somavaratan treatment during the first month with in clinic study drug administration required on Day 1 and Day 16. Twice-monthly somavaratan dosing should occur every 15 days \pm 2 days. Blood samples will be obtained on Day 8, 16, and 23 for PK and PD assessment. Blood samples on Days 1 and 16 are intended as trough samples and should be collected pre-dose. Blood samples on Day 8 and 23 are intended as peak samples and may be collected at the subject's home by an at-home health care provider. All blood sample collections should occur within \pm 1 day of the target collection day, with trough samples always collected pre-dose. In new naïve to somavaratan treatment subjects only, 12-lead ECGs shall be collected 3 days (\pm 1 day) after Day 1 dosing during the first Month (triplicate tracings).

Recording of concomitant medications, adverse events and study drug administration will be performed for all subjects.

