8.2 Analysis Populations

8.2.1 *Safety Population*

The safety population will consist of all subjects who receive any amount of study drug.

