19. Random sample tested by urine Multistix® (or similar), performed locally.
20. Somavaratan dosing commences at Day 1 with all subjects receiving twice-monthly dosing (every 15 days ± 2 days) administered in a vial and syringe configuration or with the somavaratan autoinjector (when available) subcutaneously, at room temperature, in the upper arm, abdomen, buttock or thigh.
21. Perform these assessments for subjects who terminate their participation in this study (not required for any assessments performed within the prior 14 days). For subjects who terminate the study at any time, follow up should be conducted approximately 60 days after their final study dose. This may be conducted in clinic or by telephone contact and will include the collection of adverse events and concomitant medications.

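### Subjects already on once-monthly dosing in 15VR8 switch regimen mid-study, but no switch-date baseline or period is defined, so the safety tables mix the two regimens; which date starts their visit calendar is also unclear

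*Combined protocol and SAP*

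**What the plan says.** **Purpose.** Section 3.1 says the study "will evaluate the safety of long-term twice-monthly administration of somavaratan", and Section 3.2 gives the same purpose. The primary objective in Section 2.1 concerns long-term safety of somavaratan and names no regimen.

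**Switchers.** Section 3.1 has a rule that opens "Subjects receiving somavaratan once-monthly in this study (Protocol 15VR8". It moves these subjects to the twice-monthly regimen and titrates them under Table 2. Sections 4.2 and 5 repeat the rule. The rationale for Version 2 has a subsection on rollover subjects already taking part in 15VR8, so such subjects existed at the amendment.

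**Analysis rules.** Section 5.7.2: "AEs occurring after study drug administration are treatment emergent AEs". Section 8.2.1 defines the safety population as "all subjects who receive any amount of study drug". Section 8.1 takes Baseline as the last value before the first dose in the current study and presents summaries by cohort. Section 8.5 also summarizes safety by cohort. The two cohorts are defined by oral estrogen use (Section 3.1, Table 1).

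**Calendar.** Section 3.1 says "Study visits/blood sample collections will occur every week during the first month of the study". Section 6.1.3 says "All subjects will begin twice-monthly somavaratan treatment during the first month". Appendix 1, footnote 20, says "Somavaratan dosing commences at Day 1 with all subjects receiving twice-monthly dosing".

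**The concern.** A subject who began 15VR8 on once-monthly dosing and then changed has both regimens in one study record. Every analysis anchor is the first 15VR8 dose or any study drug; none is the first twice-monthly dose. Tables meant to describe long-term twice-monthly safety would therefore include events, laboratory shifts and exposure from the regimen that Version 2 replaced. Separating tables by entry route would not help, because the mixing is within subject.

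The origin matters. The Version 2 rationale reports that, in the once-monthly Phase 2 study (15VR7), 16 of 29 subjects (55%) were above 2.0 SDS and 7 of 29 (24%) above 3.0 SDS seven days after the fifth dose. Laboratory and IGF-I changes measured from a value taken before that exposure do not describe the new regimen alone.

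There is a second, smaller question. Sites must know whether a switcher starts a new Day 1, first month and first year.

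**Working it through.** **1. The plan's own sampling count.** Table 4 gives 18 PK, 19 PD and 6 immunogenicity time-points in year one, assuming 4 months of titration.
- PK: 4 (Days 1, 8, 16, 23) + 2 × 4 (Day 1 and Day 8 at M1 to M4) + 2 × 3 (M6, M9, M12) = 18.
- PD: 18 + 1 at Screening = 19.
- Immunogenicity: D1, M1, M3, M6, M9, M12 = 6.
- Volume: 12 + 63 + 57 + 36 + 133 + 21 + 8 + 3.5 = 333.5 mL.

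All agree with Table 4.

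**2. Length of once-monthly time.** Version 1 is dated 19 November 2015 and Version 2 is dated 30 June 2016: 224 days, and 224 / 30.4375 = 7.4 months. This is the most a subject could have accrued in 15VR8 by the Version 2 date. Site start-up after Version 1 shortens it; delay in adopting Version 2 lengthens it.

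**3. A switcher followed through the analysis rules.** Take a first 15VR8 dose on the Version 1 date and a first twice-monthly dose on the Version 2 date.

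| Item | Rule | Result |
|---|---|---|
| Baseline | Section 8.1 | Value before the first once-monthly dose in 15VR8 |
| AE on day 100 | Section 5.7.2 | Treatment emergent, no regimen label |
| Safety population | Section 8.2.1 | Included from the first once-monthly dose |
| Display | Sections 8.1, 8.5 | By oral-estrogen cohort only |
| Laboratory shift at a later visit | Section 8.5 | Spans both regimens |

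Nothing in Section 8 separates the 224 days from what follows.

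**4. Calendar wording side by side.**

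| Points to study entry | Can be read as starting with titration or twice-monthly dosing |
|---|---|
| Synopsis, Study Design: weekly in the first 4 weeks of the study | Synopsis, Pharmacodynamics: month 1 of treatment; one year of quarterly sampling counted within maintenance |
| Synopsis, Immunogenicity: first year of this study | Section 3.1: titration needs weekly samples in the first month |
| Section 3.1: first month of the study | Section 6.1.3: all subjects begin twice-monthly dosing in the first month |
| Sections 6.1.1 and 6.1.2: Day 1 tied to enrollment, approval and subject number | Appendix 1, footnote 20: Day 1 tied to twice-monthly dosing |

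The right-hand column is true of switchers only if their Day 1 restarts, which no section says.

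**5. Sampling in the 12 months after the switch** (switch at study month k = 1 to 8; 4 months of re-titration assumed, as in Table 4).
- Calendar restarts: 18 PK time-points, as in step 1. ADA draws: switch day, M3, M6, M9, M12 = 5.
- Calendar runs from entry: five visits (k to k+4) × 2 = 10, plus 2 for each of study months 6, 9, 12 and 18 that falls after k+4 and by k+12. At k = 1 this is 10 + 6 = 16; at k = 5 it is 10 + 2 = 12. The range is 12 to 16. ADA draws: 3 or 4.
- Difference: 2 to 6 PK/PD time-points and 1 or 2 ADA draws. Two of the PK/PD time-points are always Days 16 and 23; the other 0 to 4 are quarterly draws. If the year counts within maintenance, as in the Synopsis PD text, those quarterly PD draws are not lost.

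**6. How many subjects.** Not stated. As an assumption only, 10 to 29 switchers would be 10/250 = 4.0% to 29/250 = 11.6% of maximum enrollment, or 10/50 = 20.0% to 29/69 = 42.0% if only the 40 new subjects joined them.

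**The case against.** The strongest defense has three parts.

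**The primary objective names no regimen, and the study is descriptive.** The Synopsis states "No formal hypothesis testing is planned for this extension study". Section 8 calls itself a brief summary, and Sections 8.1 and 9.10 promise a separate SAP that is not among the documents. A split by regimen there cannot be excluded. This stands in part: once-monthly events belong in the report. But Sections 3.1 and 3.2 describe a twice-monthly safety study, and the rules that are written pool the regimens.

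**The calendar can be read as restarting.** Switchers re-enter titration, and Section 3.1 links weekly first-month samples to titration. This stands. A reader might infer that switchers certainly miss first-month sampling on the new regimen; the documents support an ambiguity, not a definite omission. A reader might also infer that titration would be uninformed, or that Day 23 is the only seven-day response at the new interval. Neither follows: Sections 4.2 and 6.1.4 keep monthly Day 1 and Day 8 samples, and the next month's Day 8 is also a seven-day value after repeated dosing.

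**The consequences may be small.** A reader might infer that IGF-I-driven AEs will be charged to the new regimen. The Version 2 rationale says that the high values after the first Phase 2 dose were transient and without clinically important AEs, so this is possible but not shown. The 29 subjects had completed five 15VR7 doses; they are not a count of switchers, so no firm person-time total can be given.

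**Conclusion.** The analysis gap holds. Subjects change regimen within 15VR8, no switch-date anchor exists, and Baseline, treatment emergence, population and display all ignore the change. The plan should be corrected before tables are built.

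The size is up to 224 days (about 7.4 months) of once-monthly time per subject by the Version 2 date, for an unstated number of subjects. The 224 days assumes first dosing on the Version 1 date and a switch on the Version 2 date.

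The calendar problem is an inconsistency to reconcile. On the study-entry reading it costs Days 16 and 23 of the first month after the switch, plus some quarterly PK/PD and ADA draws. It would also be too strong to say that all first-year sampling is shortened by the time already served, because the first year is tied to the study for ADA but placed within maintenance in the Synopsis PD text.

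**What to change.** **Analysis (Sections 8.1, 8.2.1, 8.5 and the SAP).**
- Start the twice-monthly period at the first twice-monthly dose.
- For in-study switchers, add a switch-date baseline, the last value before that dose, and use it for changes and shifts in that period. State how old the value may be: in the first year laboratory panels are quarterly, so it could be about three months old.
- Base twice-monthly TEAE tables on events with onset on or after the first twice-monthly dose, and state how an event that starts earlier and worsens later is assigned.
- Report exposure, TEAEs and laboratory data before that date as a separate once-monthly period. Nothing is dropped.

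**Calendar.** Reconcile the Synopsis (Study Design, Immunogenicity, Pharmacodynamics), Sections 3.1 and 6.1.1 to 6.1.3, and Appendix 1 on which date starts the first month and first year for in-study switchers. The choice is for the sponsor.

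**Cost.** Wording and extra table columns; dose administration is already documented (Section 4.9.1). If the reconciled calendar restarts, each switcher gives about 2 to 6 more PK/PD samples and 1 or 2 more ADA samples over 12 months. Safety laboratory panels, which Appendix 1 schedules at the same quarterly visits, would increase similarly.
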